8.3.1. Efficacy Analyses

All efficacy analyses will be performed on the mITT population. Selected analyses may be performed on the Per-Protocol population.

Baseline and change from baseline at each posttreatment visit will be summarized for all numerical variables with descriptive statistics. Frequency and percentage will be calculated for categorical variables. The nominal p-values along with the 95% confidence intervals (CI) will be provided as appropriate. For subjects who have both eyes affected, the change from baseline will be determined based on the eye with the worst severity at baseline. If both eyes have the same severity at baseline, the right eye will be used to determine change from baseline.

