2.1. Assessments of Efficacy

Table 2: Efficacy Assessments for Study MNK14084113

Efficacy Assessments	
Corneal Staining	Inferior, superior, central and total cornea regions as measured by the Ora Calibra™ Corneal Staining Scale (0 - 4)
Conjunctival Staining	Nasal, temporal and total conjunctiva regions as measured by the Ora Calibra™ Conjunctival Staining Scale (0-4)
Conjunctival Redness	As measured by the Ora Calibra™ Conjunctival Redness Scale (0 - 4)
Tear Production	Schirmer's Test (mm)
Tear Film Stability	Tear Film Break-Up Time (seconds)
Dryness	As measured by the 0 - 100 mm Visual Analogue Scale (VAS)
Ocular Discomfort	As measured by the Ora Calibra™ Ocular Discomfort Scale (0 - 4)
Ocular discomfort, dryness, grittiness, burning and stinging	As measured by the Ora Calibra™ 4-symptom Questionnaire (0 - 5)
Quality of Life	As measured by IDEEL (Impact of Dry Eye on Everyday Life)
Immunological protein assay	Protein assay to detect levels of the cytokine array [interleukin 1,6,17; interferon- γ]; ratio of T helper cells to T regulatory cells

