4.1. Inclusion Criteria

To be eligible to participate in the study, at the Screening Visit and the Baseline Visit (except as noted below) each subject must:

1. Be adequately informed and understand the nature and risks of the study and must be able to provide a signature and date on the ICF;
2. Be 18 years of age or older at the Screening Visit and may be male or female;
3. Have normal lid anatomy;
4. Have a reported history of severe keratitis in one or both eyes and a history of previous treatment for keratitis within the previous 6 months;
5. Did not respond adequately or did not tolerate previous treatment with topical cyclosporine or LFA-1 antagonist;
6. Have all the following in at least one eye (the same eye) at screening and baseline:
 - a. Have an inferior corneal fluorescein staining score of at least 2 points in any field (Ora Calibra™ Scale) in at least one eye at the Screening and Baseline visits;
 - b. Have a sum corneal fluorescein staining score ≥ 4 , based on the sum of the central, superior, and inferior regions of the cornea (Ora Calibra™ Scale) in at least one eye at the Screening and Baseline Visits;
 - c. Have a sum lissamine green conjunctival score of ≥ 2 , based on the sum of the temporal and nasal regions of the conjunctiva (Ora Calibra™ Scale) in at least one eye at Screening and Baseline visits;
 - d. Have a conjunctival redness score ≥ 1 (0-4 point Ora scale) in at least one eye at the Screening and Baseline Visits;
 - e. Have a Schirmer score ≥ 1 mm and ≤ 10 mm/5min in at least one eye at the Screening and Baseline Visits;
 - f. Have an Ocular Discomfort Score (ODS) of ≥ 2 (0-4 point Ora scale) in at least one eye at the Screening and Baseline Visits;
7. If female, of nonchildbearing potential (history of hysterectomy, bilateral oophorectomy, bilateral tubal ligation; or postmenopausal with no history of menstrual flow in the 12 months prior to the Screening Visit); or, if of childbearing potential, be nonpregnant, nonlactating, and agree to use 2 forms of effective contraception when with a male partner for the duration of the study (through Visit 6). Acceptable forms of contraception include hormonal measures (oral contraceptive pills, contraceptive patch, contraceptive ring, injections), intrauterine devices, double barrier method (condom plus diaphragm, condom or diaphragm plus spermicidal gel or foam, surgical sterilization of the male partner), and abstinence;

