7.1.4. T-Cell Assessments

Blood samples for T-cell assessments (T-cell effector total number, T-cell regulatory, and regulatory/effector T-cell ratio) will be collected at specified times during the study and shipped to a central laboratory. Detailed instructions for the collection, handling, storage and shipment of the samples will be provided in a separate laboratory manual.

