8. STATISTICAL CONSIDERATIONS

8.1. Sample Size Determination

Approximately 36 subjects will be screened in order to have 30 analysable subjects enrolled in this study. No formal sample size calculations will be performed. The sample size was determined empirically.

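### Section 8.3.1: choosing the worse eye at Baseline and measuring change from that same reading adds an avoidable bias toward improvement for some ocular signs, on top of that from the entry thresholds

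*Combined protocol and SAP*

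**What the plan says.** Section 8.3.1 provides that, for subjects with both eyes affected, "the change from baseline will be determined based on the eye with the worst severity at baseline"; ties go to the right eye. Baseline is Visit 2, Day 1 (Synopsis and Table 1). The supplied text does not say which sign, score or composite severity means. The same section plans "The nominal p-values along with the 95% confidence intervals", to be given where appropriate, and names no test.

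Bilateral disease is foreseen: criterion 4 of Section 4.1 reads "Have a reported history of severe keratitis in one or both eyes". Criterion 6 of that section applies its sign thresholds at both pre-treatment visits: "Have all the following in at least one eye (the same eye) at screening and baseline". Section 5.4 confirms an open-label design without randomization. Section 8.3 defers detail to a separate SAP, which was not supplied.

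**The concern.** When the sign being analysed also ranks the eyes, one reading does two jobs: it selects the eye and it is the value from which change is counted. The selected reading carries, on average, visit error in the bad direction. That error is not repeated at the next visit, so the eye appears to improve without any drug effect, and no control arm cancels this.

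At stake is the reading of the ocular signs in Table 2. A nominal p below 0.05 on a staining or redness score could be taken as evidence of benefit when part of the change was built in by the choice of eye. Because severity is undefined, the analysis eye could also differ from one endpoint to the next.

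**Working it through.** The plan gives no SD, reliability, effect size or power, so there is no figure of its own to reproduce.

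**Inputs from the plan.** n = 30, from Section 8.1: "Approximately 36 subjects will be screened in order to have 30 analysable subjects enrolled in this study". The eye and tie rules are from Section 8.3.1, the thresholds at Screening and Baseline from criterion 6, and the 0-4 grades from Table 2 and Section 7.1.3.

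**Assumed.** Eye score variance is 1, made up of a true part of 0.7 and visit error of 0.3. The true between-eye correlation is 0.8. Visit errors are independent between eyes and visits unless stated. There is no true change, and the test is a two-sided 5% paired t-test. Bilateral subjects number 8, 15 or 30 of 30.

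**Step 1: spurious change, no threshold, endpoint ranks its own eyes.**
- Variance of the between-eye difference: 2 × 0.7 × (1 − 0.8) + 2 × 0.3 = 0.28 + 0.60 = 0.88; SD 0.938.
- Expected excess of the worse eye over the mean of the two: 0.938 × √(2/π) / 2 = 0.374.
- Share of that excess due to visit error: 0.60 / 0.88 = 0.682.
- Spurious improvement per bilateral subject: 0.374 × 0.682 = 0.255 SD.
- Averaged over the sample: × 8/30 = 0.068 SD; × 15/30 = 0.128 SD; all bilateral 0.255 SD.

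**Step 2: rejection rate.** The second moment of change stays at 2 × 0.3 = 0.6.
- All bilateral: SD = √(0.6 − 0.255²) = 0.731; SE = 0.731/√30 = 0.1335; noncentrality = 0.255/0.1335 = 1.91; rejection about 45%.
- Half bilateral: SD 0.764; SE 0.1395; noncentrality 0.1276/0.1395 = 0.91; rejection about 14%.
- A quarter bilateral (8 of 30): about 7%.

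Simulation agrees. Over reliability 0.6-0.9 and true eye correlation 0.7-0.9 the ranges are 6%-8% (quarter), 8%-17% (half) and 20%-57% (all). If the two eyes' visit errors correlate 0.5, the rates fall to 6%, 8% and 19%.

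**Step 3: adding an entry threshold on the same sign (simulated rejection rates, continuous score).** The Screening rule picks the Screening-worse eye among qualifying eyes.

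| Threshold | Threshold alone | Half bilateral: 8.3.1 / Screening rule | All bilateral: 8.3.1 / Screening rule |
|---|---|---|---|
| none | 5% | 14% / 5% | 45% / 5% |
| mean | 21% | 42% / 23% | 67% / 24% |
| +0.5 SD | 37% | 58% / 40% | 77% / 43% |
| +1 SD | 58% | 73% / 61% | 87% / 62% |

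In SD units the thresholds alone give 0.16, 0.22 and 0.29. The eye choice adds 0.07, 0.06 and 0.04 (half bilateral) or 0.15, 0.12 and 0.10 (all). The threshold part is the larger one throughout. With between-eye visit-error correlation 0.5, threshold +0.5 SD and half bilateral, the comparison is about 51% against 38%.

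**Step 4: integer 0-4 grade with right-eye ties.** With an assumed mean of 2.0, SD 0.9 and entry grade of at least 2, about 41% of bilateral subjects tie. Rejection is about 33% against 15% (half bilateral) and 57% against 16% (all). A variant of the half-bilateral model gave 35% against 17%, falling to 26% against 15% with visit-error correlation 0.5.

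**Step 5: reach.** If severity is one other measure with unrelated visit error, the added bias is 0.00 SD and rejection (no threshold) is 5%. Tear film break-up time has no threshold in criterion 6. If severity is read endpoint by endpoint, and break-up time's visit error is unrelated to that of the thresholded signs, the eye rule is its only selection effect: 13% (half) and 45% (all) against 5%.

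**Step 6: eye agreement.** The correlation of the between-eye difference across the two visits is 0.28/0.88 = 0.318. The Screening-worse eye is therefore also the Baseline-worse eye with probability 1 − arccos(0.318)/π = 0.60.

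**The case against.** The strongest reply is about attribution. A reader might infer that the eye rule is the reason the nominal p-values do not test a treatment effect. The documents do not support that. An uncontrolled trial that applies entry thresholds at Baseline could not isolate a treatment effect under any eye rule: after the Screening rule, 23% to 62% rejection remains on thresholded signs in Step 3. The eye rule is an increment to an existing limitation.

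Reach is the second reply, and it also stands. Worst severity can naturally be read as one overall judgement per subject, in which case only the ranking sign and those sharing its visit error are affected. The break-up-time case needs the endpoint-by-endpoint reading. Subject-level measures are outside the rule, including the blood measures in Table 2 ("Protein assay to detect levels of the cytokine array") and Section 7.1.4 ("Blood samples for T-cell assessments"). The p-values are already called nominal, and no test is fixed, so they may not be produced for every sign.

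Third, coarse grades, ties and correlated visit errors shrink the effect. They do, but Step 4 shows that a clear increment survives.

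Fourth, the separate SAP may define severity or the study eye. It may, but a definition alone leaves the bias while the Baseline reading still both selects the eye and starts the change.

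**Conclusion.** The point holds as a limited but avoidable bias. Its direction is toward improvement for any sign that defines severity or shares its visit error, in bilaterally affected subjects, whenever readings carry visit error. Its size cannot be fixed from the documents, because reliability, between-eye correlation, the bilateral share and the meaning of severity are all absent. Under the assumptions above, the increment in false rejection on a thresholded integer grade is about 18 percentage points with half the subjects bilateral (33% − 15%) and 41 with all bilateral (57% − 16%). It is smaller if the two eyes' visit errors are correlated, and nil for signs whose error is unrelated to the ranking measure.

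A reader might also infer that the trial's main efficacy result is biased by this rule. It is not. Section 2.3 makes the proportion of IDEEL responders the sole primary outcome, with no secondary outcomes, and IDEEL is scored per subject. Subjects with one affected eye are likewise untouched. The change is worth making because it is cheap, not because the study's primary conclusion depends on it.

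**What to change.** 1. In Section 8.3.1, and identically in the separate SAP, define one study eye per subject for all eye-level endpoints. Suggested wording: *If only one eye meets inclusion criterion 6, that eye is the study eye. If both meet it, the study eye is the one with the worse [one named measure, for example sum corneal fluorescein staining] at Screening (Visit 1), or the right eye if tied. Baseline is the Visit 2 value of the study eye.* The sponsor may name another measure. In simulation, ranking on the endpoint itself or on a different sign left the same residual (0.23 SD each; half bilateral, threshold +0.5 SD).

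2. State that eligibility still uses Baseline data, including where only one eye qualifies. The change removes nearly all of the eye-choice bias but leaves the threshold part.

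3. Present eye-level change from baseline descriptively, or state that its nominal p-values and confidence intervals include regression to the mean and do not isolate a treatment effect.

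The cost is wording only, since Table 1 already schedules these signs at Visit 1. The downside is that, at reliability 0.7 and true eye correlation 0.8, the Screening-worse eye is also the Baseline-worse eye in only about 60% of bilateral subjects. Apparent improvements will also be smaller.

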8.3.2. Safety Analyses

All safety data will be summarized with descriptive statistics or frequency tables as appropriate. Safety analyses will be performed on the safety population. Safety endpoints include the incidence and severity of ocular AEs, incidence and severity of other AEs, new or worsening cataracts, and the mean change in IOP.

AEs will be coded using MedDRA version 22.0 by preferred term within system organ class. The number of AEs and the number of subjects reporting AEs will be listed and summarized descriptively by system organ class, preferred term, severity, and causality for each treatment group. Only treatment-emergent adverse events (TEAE) (events that are new in onset or aggravated in severity following treatment) will be included in all summaries. Serious adverse events (SAE) (including death) will be summarized.

Other safety assessments include vital signs (heart rate, diastolic/systolic blood pressures, respiratory rate, and body temperature), clinical laboratory tests, ophthalmology examinations, physical examinations, HbA1c, pregnancy test, hepatitis serology, IGRA for TB, etc. All of these assessments will be listed and summarized descriptively.

8.3.3. Interim Analyses

No formal interim analyses are planned for this study.

8.3.4. Handling Missing Data

A full description of the missing data imputation method for all endpoints will be described in the statistical analysis plan.

9. SUPPORTING DOCUMENTATION AND OPERATIONAL CONSIDERATIONS

9.1. Appendix 1: Regulatory, Ethical, and Study Oversight Considerations

9.1.1. Regulatory and Ethical Considerations

The study will be conducted in full compliance with applicable international, national and local regulatory requirements; US Food and Drug Administration (FDA) regulations including 21 Code of Federal Regulations (CFR) 314.106 and 312.120, (where applicable), ICH guidelines for GCP, in accordance with the ethical principles that have their origins in the Declaration of Helsinki, and European regulation 536/2014/EU (where applicable).

It is the responsibility of the investigator to obtain the approval of the Institutional Review Board (IRB)/Independent Ethics Committee (IEC) before the start of the study. A copy of the approval letter along with a roster of IRB/IEC members and compliance letter and/or the US Department of Health and Human Services general assurance number (if applicable) will be provided to the sponsor and retained as part of the study records. During the course of the study, the investigator will provide timely and accurate reports to the IRB/IEC on the progress of the study at appropriate intervals (not to exceed 1 year) and at the completion of the study. The investigator will notify the IRB/IEC of SAEs or other significant safety findings per IRB/IEC guidelines. The study protocol, ICF, advertisements (if any), and amendments (if any) will be approved by the IRB/IEC in conformance with international, national and local regulatory requirements.

Any change in the study plan requires a protocol amendment. An investigator must not make any changes to the study without IRB/IEC and sponsor approval except when necessary to eliminate apparent immediate hazards to the subjects. A protocol change intended to eliminate an apparent immediate hazard to subjects may be implemented immediately, but the change must then be documented in an amendment, reported to the IRB/IEC within 5 working days, and submitted to the appropriate regulatory agency in the required time frame, if appropriate.

9.1.2. Financial Disclosure

Investigators and subinvestigators will provide the sponsor with sufficient, accurate financial information as requested to the sponsor to submit complete and accurate financial certification or disclosure statements to the appropriate regulatory authorities. Investigators are responsible for providing information on financial interests during the course of the study and for 1 year after the end of the study.

9.1.3. Subject Information and Consent

The ICF must be approved by the sponsor and the IRB/IEC before any subject provides consent. The investigator will provide Mallinckrodt with a copy of the IRB/IEC-approved ICF and a copy of the IRB/IEC's written approval before the start of the study.

At the Screening Visit (and at other time as may be required by the study or when changes are made to the consent form), subjects will read the consent form(s) and any privacy authorization as required by local and national regulations (such as the Health Insurance Portability and Accountability Act [HIPAA] authorization form), if applicable after being given an explanation

of the study. Before signing the consent form(s) and the privacy authorization form (if applicable), subjects will have an opportunity to discuss the contents of these forms with study site personnel.

Subjects must assent understanding of and voluntarily sign these forms in compliance with ICH GCP and all applicable national and international regulations, before participating in any study-related procedures. Subjects will be made aware that they may withdraw from the study at any time. Subjects unable to give written informed consent must orally assent to the procedures, and written informed consent must be obtained from a legally authorized representative in accordance with national and local laws, as applicable.

The ICF must contain all applicable elements of informed consent and the mandatory statements as defined by national and local regulations including confidentiality. All versions of each subject's signed ICF must be kept on file by the site for possible inspection by regulatory authorities and/or authorized Mallinckrodt personnel. Signed copies of the consent form(s) and the HIPAA authorization form, if applicable, will be given to the subject.

The subjects will be made aware of their right to see and copy their records related to the study for as long as the investigator has possession of this information. If the subject withdraws consent and/or HIPAA authorization, the investigator can no longer disclose health information, unless it is needed to preserve the scientific integrity of the study.

9.1.4. Data Protection

Study subjects will be assigned a unique identifier by the sponsor or designee. Any subject records or datasets that are transferred to the sponsor will contain the identifier only; subject names or any information which would make the subject identifiable will not be transferred.

The subject must be informed that his/her personal study-related data will be used by the sponsor in accordance with local data protection law. The level of disclosure (in accordance with local and/or national law) must also be explained to the subject.

The subject must be informed that his/her medical records may be examined by Clinical Quality Assurance auditors or other authorized personnel appointed by the sponsor, by appropriate IRB/IEC members, and by inspectors from regulatory authorities.

9.1.5. Committees Structure

No monitoring committees will be used for this study.

9.1.6. Dissemination of Clinical Study Data

Study results and de-identified individual subject data will be protected as required by local and/or national regulation.

9.1.7. Data Quality Assurance

The sponsor performs quality control and assurance checks on all clinical studies that it sponsors. Before enrolling any subjects in this study, sponsor personnel and the investigator review the protocol, the Prescribing Information ([Mallinckrodt Package Insert, 2019](#)), the electronic case report forms (eCRF) and instructions for their completion, the procedure for obtaining informed consent, and the procedure for reporting AEs and SAEs. A qualified representative of the sponsor will monitor the conduct of the study.

The investigator will permit study-related monitoring, audits, IRB review, and regulatory inspections by providing direct access to original source data and documents.

Each subject's eCRF should be fully completed and submitted to the Sponsor in a timely fashion.

If an investigator retires, relocates, or otherwise withdraws from conducting the study, the investigator must notify the sponsor to agree upon an acceptable storage solution. Regulatory agencies will be notified with the appropriate documentation.

Any significant changes in study personnel will require an updated Statement of Investigator (ie, FDA form 1572) to be filed with the sponsor.

The investigator must notify their IRB of protocol deviations in accordance with local regulatory and IRB requirements.

The eCRF data are stored in a database and processed electronically. The sponsor's MM reviews the data for safety information. The data are reviewed for completeness, and logical consistency. Automated validation programs will identify missing data, out-of-range data, and other data inconsistencies. In addition, clinical laboratory data will be processed electronically. Requests for data clarification are forwarded to the study site for resolution.

9.1.8. Source Documents

All subject information recorded in the eCRF will be attributable to source data from the investigational site.

The investigator shall retain and preserve 1 copy of all data collected or databases generated in the course of the study, specifically including but not limited to those defined by GCP as essential. Essential documents should be retained until at least 2 years after the last approval of a marketing application in an ICH region and until there are no pending or contemplated marketing applications in an ICH region or at least 2 years have elapsed since the formal discontinuation of clinical development of the investigational medicinal product. These documents should be retained for a longer period, however, if required by the applicable regulatory requirements or by an agreement with the sponsor. It is the responsibility of the sponsor to inform the investigator/institution as to when these documents no longer need to be retained. Prior to destruction of any study essential documents, the investigator must first obtain written approval from the sponsor.

